## Part A: Single Ascending Dose | Healthy Participants (Cohort 2)

Procedure	Treatment Periods 4 to 6														
	Day -1	Day 1												Day 2 (D1+24h)	Day 3 (D1+ 48h)
		Pre-dose	0	5m	30m	45m	1h	2h	4h	6h	8h	12h	16h		
Admission to Clinical Unit	X														
Discharge															X
Phone Call															
Brief Physical Examination	X														X
Inhaler Training 	X														
Alcohol and Smoking Breath Test	X														
Urine Drug Screen	X														
COVID-19 Test 	X														X
Urine Pregnancy Test	X														
Randomisation		X													
Treatment Administration 			X												
AE Review				←											→
SAE Review			←												→
Concomitant Medication Review				←											→
Spirometry (FEV1 and FVC) 		X						X							
Vital Signs 	X	X			X		X		X			X			X
12-Lead Safety ECG 	X	X		X	X		X		X			X			X
Telemetry 			←												
CCI															
Laboratory Safety Assessment 	X														X
PK Blood Sample			X		X	X	X	X	X	X	X	X	X		X
CCI															

**Footnotes to Part A: Single Ascending Dose | Healthy Participants (Cohort 2)**

1. Day -1 inhaler training may be performed on Day 1 if needed and before administration of the first dose. Additional training may be provided as needed and according to Investigator discretion.
2. To be performed according to local site procedures. Additional ad hoc testing may be implemented based on local site procedures.
3. No meals from 2 hours before dosing until 2 hours post dose.
4. Perform in triplicate and includes FEV1 and FVC.
5. Includes systolic and diastolic blood pressure, heart rate, respiration rate and tympanic temperature.
6. On Day 1 pre-dose of each treatment period, triplicate ECG measurements will be collected, and the mean values will be used to calculate baseline. At all other time points single ECGs will be taken.
7. Cardiac telemetry to start approximately 1-hour pre-dose and continuously until 6 hours post dose.

CCI

9. Clinical Chemistry and Haematology only.

CCI

**Part B: Repeat Dose | Healthy Participants (Cohorts 3 and 4)**

[figure not shown]
Procedure	Inpatient Period																	
	D-1	D1	D2	D3	D4	D5	D6	D7	D8	D9	D10	D11	D12	D13	D14	D15 (D14+ 24h)	D16 (D14+ 48h)	D17 (D14+ 72h)
Admission to Clinical Unit	X																	
Discharge																		X
Brief Physical Examination	X		X													X		X
Inhaler Training 	X																	
Alcohol and Smoking Breath Test	X																	
Urine Drug Screen	X																	
COVID-19 Test 	X					X									X			X
Urine Pregnancy Test	X																	
Randomisation		X																
Treatment Administration		X	X	X	X	X	X	X	X	X	X	X	X	X	X			
AE Review		←————→																
SAE Review		←————→																
Concomitant Medication Review		←————→																
Spirometry (FEV1 & FVC)		X 	X															
Vital Signs 	X	X 	X		X													
12-Lead Safety ECG 	X	X	X		X		X		X		X		X		X	X		X
Telemetry		X 																

Procedure	Inpatient Period																		
	D-1	D1	D2	D3	D4	D5	D6	D7	D8	D9	D10	D11	D12	D13	D14	D15 (D14+ 24h)	D16 (D14+ 48h)	D17 (D14+ 72h)	D18 (D14+ 96h)
CCI																			
Laboratory Safety Assessment 	X		X 		X 		X 		X 		X 		X 		X 		X		X
PK Blood Sample		X 	X 	X 	X 	X 	X	X	X										
CCI																			

**Footnotes to Part B: Repeat Dose Repeat Dose | Healthy Participants (Cohorts 3 and 4)**

1. Day -1 inhaler training may be performed on Day 1 if needed and before administration of the first dose. Additional training may be provided as needed and according to Investigator discretion.
2. To be performed according to local site procedures. Day 4 to 6 test is required for Cohort 4 only ahead of bronchoscopy on Day 7. Day 12 to 14 test is required for Cohort 3 only ahead of bronchoscopy on Day 15. Additional ad hoc testing may be implemented based on local site procedures.
3. Predose and 1-hour post-dose only.
4. Includes systolic and diastolic blood pressure, heart rate, respiration rate and tympanic temperature.
5. Predose.
6. On treatment days ECGs will be collected at predose and 6-hours post-dose. On Day 1 predose, triplicate measurements will be collected, and the mean values will be used to calculate baseline. At all other times single ECGs can be taken.
7. Cardiac telemetry to start approximately 1-hour pre-dose and continuously until 6 hours post dose.

CCI

9. Clinical Chemistry and Haematology at all visits. Coagulation will be assessed on Day 4 for both cohorts.
10. At pre-dose, 5 min, 30 min, 45 min, 1 h, 2 h, 4 h, 6 h, 8 h, 12 h and 16 h.

CCI

16. At 15 min.

**Part C: Repeat Dose | Asthma (Cohort 5)**

Procedure	Inpatient Period								
	D-1	D1	D2	D3	D4	D5	D6	D7	D8 (D7+ 24h)
Admission to Clinical Unit	X								
Discharge									X
Review Inclusion and Exclusion Criteria	X								
Brief Physical Examination	X		X						X
Inhaler Training 	X								
Alcohol and Smoking Breath Test	X								
Urine Drug Screen	X								
COVID-19 Test 	X								X
Urine Pregnancy Test	X								
Randomisation		X							
Treatment Administration		X	X	X	X	X	X	X	
AE Review		↔							
SAE Review		↔							
Concomitant Medication Review		↔							
Spirometry (FEV1 & FVC)		X 	X 	X 	X 	X 	X 	X 	X
PEF 	X 	X	X	X	X	X	X	X	X
Vital Signs 	X	X 	X 	X 	X 	X 	X 	X 	X
12-Lead Safety ECG 	X	X	X		X		X	X	X
Telemetry		X 							
Laboratory Safety Assessment 	X		X 		X 		X 		X
PK Blood Sample		X 	X 	X 	X				

**Footnotes to Part C: Repeat Dose | Asthma (Cohort 5)**

1. Day -1 inhaler training may be performed on Day 1 if needed and before administration of the first dose. Additional training may be provided as needed and according to Investigator discretion.
2. To be performed according to local site procedures. Additional ad hoc testing may be implemented based on local site procedures.
3. Predose and 30 min only.
4. PEF measurements will be taken in triplicate twice each day (once in morning upon waking and once in the evening before bedtime) from Day -1 evening until discharge on Day 8. Clinical site staff will complete and record the PEF measurements at each time point.
5. Provide PEF device refresher training if necessary.
6. Includes systolic and diastolic blood pressure, heart rate, respiration rate and tympanic temperature.
7. Predose only
8. On treatment days ECGs will be collected at predose and 6-hours post-dose. On Day 1 predose, triplicate measurements will be collected, and the mean values will be used to calculate baseline. At all other times single ECGs can be taken.
9. Cardiac telemetry to start approximately 1-hour pre-dose and continuously until 6 hours post dose.
10. Clinical Chemistry and Haematology only.
11. At pre-dose, 5 min, 15 min, 30 min, 45 min, 1 h, 2 h, 4 h, 6 h, 8 h, 12 h and 16 h

## 2. INTRODUCTION

Phosphatidylinositol 4-kinase beta (PI4KB) is a human intracellular lipid kinase that catalyses the formation of phosphatidylinositol-4-phosphate (PI4P), a key component of the Golgi and trans-Golgi network membranes and regulator of trafficking to and from the Golgi body.

PI4KB is a host factor required for the replication of multiple picornaviruses, including human rhinovirus (HRV). Following cell entry, HRV proteins produced by translation of viral RNA recruit PI4KB to the Golgi membrane, where increased synthesis of PI4P drives membrane cholesterol enrichment. The role of PI4KB is crucial for viral polyprotein processing and for the formation of replication organelles where viral replication takes place [Hsu, 2010; Altan-Bonnet, 2012; Roulin, 2014].

GSK3923868 is a selective and potent inhibitor of PI4KB being developed for respiratory disease and specifically the treatment of rhinovirus associated exacerbations of chronic obstructive pulmonary disease (COPD) and asthma. GSK3923868 is not an immunomodulatory drug.

### 2.1. Study Rationale

This is a first time in human (FTIH) study designed to evaluate the safety, tolerability and pharmacokinetic (PK) profile of single and repeat inhaled doses of GSK3923868 in both healthy participants and asthmatics. The study will use the Monodose RS01 inhaler for drug delivery. This study aims to evaluate the safety and tolerability profile of the molecule and will also obtain preliminary information regarding PK to support future clinical development.

### 2.2. Background

HRV are small, non-enveloped, positive sense RNA viruses belonging to the family *Picornaviridae* and genus *Enterovirus*. The characteristic clinical manifestation of HRV infection is the common cold, for which HRV is responsible for approximately 50% of cases, though during seasonal peaks in autumn and spring, incidence can be up to 80% [Turner, 2007].

The symptoms related to HRV infection are generally limited to the upper respiratory tract (e.g. rhinorrhoea, sore throat, sneezing) and of minimal clinical concern. However, in the context of chronic respiratory diseases, such as COPD and asthma, HRV has been shown to induce lower respiratory tract symptoms (e.g. cough, wheeze and shortness of breath) and is the predominant viral stimulus leading to exacerbations [Hershenson, 2013]. Furthermore, HRV infection may increase host susceptibility to secondary bacterial infection by upregulation of cell surface receptors, disruption of normal epithelial barrier function and through impairment of macrophage response following exposure to bacterial toll-like receptors [Jacobs, 2013].

Preclinical data support the use of GSK3923868 in the treatment of HRV infection. In air-liquid interface cultures of fully differentiated human bronchial epithelial cells, GSK3923868 has been shown to exhibit potent and slowly reversible inhibition of HRV

replication ( $t_{1/2} \sim 50$  h via washout protocol). *In vitro* data also indicates that GSK3923868 is a potent inhibitor of viral replication in a broad number of HRV strains from both major and minor groups (HRV-A and HRV-B species,  $IC_{50}$  range 0.3 to 3.9 nM). In other experiments, HRV-C species have also been shown to be sensitive to PI4KB inhibition [[Mello, 2014](#)].

There are currently no licensed treatments or vaccines for HRV, with previous treatments generally targeting virus-specific factors including capsid binding and cell entry or inhibition of viral enzymes (e.g. 3C protease) necessary for viral genome processing and replication. The failure to develop an effective treatment has been attributed to the antigenic diversity of HRV which has over 160 serotypes and also the rapid emergence of drug resistance [[Casanova, 2018](#)]. As PI4KB inhibition is a host target, it is expected to exhibit a comparably higher barrier to resistance.

As a selective and potent inhibitor of PI4KB, GSK3923868 has the potential to inhibit viral replication whilst permitting normal immune mediated clearance of the virus. This could lead to reduced symptoms, prevention of HRV driven exacerbations and prevention of secondary bacterial infections.

A detailed description of the chemistry, preclinical pharmacology, efficacy and safety of GSK3923868 is provided in the Investigator's Brochure [GSK Document Number [2020N427621\\_00](#)].

### **2.3. Benefit/Risk Assessment**

More detailed information about the known and expected benefits and risks and reasonably expected adverse events of GSK3923868 may be found in the Investigator's Brochure [GSK Document Number [2020N427621\\_00](#)].

### 2.3.1. Risk Assessment

Potential Risk of Clinical Significance	Summary of Data/Rationale for Risk	Mitigation Strategy
Study Intervention [GSK3923868]		
Bronchospasm	Can potentially occur with any inhaled treatment.	
Inclusion/Exclusion criteria: In Parts A and B healthy participants with an FEV1 and an FVC < 80% of predicted normal value will be excluded. In Part C only participants with mild to moderate asthmatics with a pre-bronchodilator FEV1 > 65% of predicted normal value will be recruited.
 
Monitoring: All doses of study treatment will be administered in the clinical pharmacology unit in the presence of clinical staff. Spirometry will be conducted pre and post dose to monitor participants.
 
Management: Treatment with a short-acting inhaled bronchodilator will be available. If bronchospasm occurs GSK3923868 will be discontinued immediately. The participant will be assessed and, if necessary, further therapy will be given as deemed appropriate by the Investigator or the attending physician.
 
Participants will be withdrawn from the study if bronchospasm occurs.

Respiratory tract irritancy	In rats dosed for 4 weeks by inhaled administration, microscopic findings were noted in the lungs and bronchi, with minimal degeneration/regeneration of the epithelium at	Appropriate safety margin: Maximum clinical exposure at 3 mg are expected to be below the

Potential Risk of Clinical Significance	Summary of Data/Rationale for Risk	Mitigation Strategy
	
the bronchioloalveolar junction at 2060 µg/kg/day. In addition, an increased incidence of inflammatory cell infiltrate (minimal or slight severity), composed predominantly of granulocytes, of the peribronchiolar/perivascular interstitium was also seen at 2060 µg/kg/day. Minimal or slight inflammatory cell infiltrate was seen at a higher than control incidence in females given 2060 µg/kg/day only. However, no microscopic findings in dog IH and rat IV studies.
	
NOAEL exposure margins (AUC: 15-fold; Cmax: 5-fold; lung deposition: 5-fold).
 
Monitoring: respiratory AEs will be monitored and spirometry will be conducted pre- and post-dosing in all three parts of the study. In addition, peak expiratory flow (PEF) monitoring will be implemented for asthmatics in Part C.
 
Sentinel dosing will be used at each dose escalation (Part A), and also for one of the repeat dose cohorts (Part B). Escalation will only proceed after a blinded review of safety, tolerability and plasma PK obtained in at least 5 participants on active treatment at the prior dose level.

Study Procedures		
Spirometry assessments	Shortness of breath, coughing, light headedness or fainting, and/or chest tightness during the spirometry assessments.	As specified in the informed consent form for this study, if any of these symptoms should occur, the participant will receive appropriate medical treatment.
CCI		

Potential Risk of Clinical Significance	Summary of Data/Rationale for Risk	Mitigation Strategy
	CCI	

### **2.3.2. Benefit Assessment**

No clinical benefit is expected for the healthy participants or asthma patients enrolled in this FTIH study, as evidence for the potential of clinical benefits of GSK3923868 is yet to be determined. Furthermore, clinical benefit would not be expected in participants not experiencing a human rhinovirus infection.

However, participants may benefit in the knowledge that they are contributing to the process of developing new therapies in an area of unmet need. Participants may also benefit from the thorough medical assessments they receive during the course of the study.

### **2.3.3. Overall Benefit: Risk Conclusion**

This study will be conducted in a fully equipped clinical pharmacology unit with access to hospital emergency facilities. Considering the measures taken to minimise the potential risks associated with participation in this study, the enrolment of healthy participants and stable asthma patients is considered justified by the anticipated benefits that may be afforded to participants with COPD and Asthma in the future.

### 3. OBJECTIVES AND ENDPOINTS

#### 3.1. Objectives and Endpoints: Parts A and B (Healthy Participants)

Objectives	Endpoints
Primary	

 
To evaluate the safety and tolerability of GSK3923868 following single and repeat inhaled administration in healthy participants.
 
	
 
Adverse events (AEs) and serious adverse events (SAEs).
 
Clinically significant laboratory values, vital signs, 12-lead electrocardiogram (ECG) and spirometry measurements up to Day 2 of the final treatment period in Part A, and Day 18 in Part B.
 

Secondary	
Derived pharmacokinetic parameters as data permit, including (but not limited to):
 
Single dose (Part A, Cohorts 1 & 2):
 
 
Area under the plasma GSK3923868 concentration versus time curve from time zero to last quantifiable concentration (<math>AUC(0-t)</math>) and from time zero to infinity (<math>AUC(0-\infty)</math>) (if determined).
 
Maximum observed GSK3923868 plasma concentration (<math>C_{max}</math>).
 
Time to maximum observed plasma drug concentration (<math>T_{max}</math>).
 
 
Repeated dose (Part B, Cohorts 3 & 4):
 
 
<math>AUC(0-\tau)</math> on Day 1 and Day 14 (<math>\tau=24h</math> for once a day dosing regimen) (if determined).
 
<math>C_{max}</math> and <math>T_{max}</math> on Day 1 and Day 14.
 

CCI

Objectives	Endpoints
CCI	

### 3.2. Objectives and Endpoints: Part C (Participants with Asthma)

Objectives	Endpoints
Primary	

 
To evaluate the safety and tolerability of GSK3923868 following repeat inhaled administration in participants with asthma.
 
	
 
AE and SAEs
 
Clinically significant laboratory values, vital signs, 12-lead ECG and spirometry measurements up to Day 8.
 

Secondary	

 
To evaluate the plasma pharmacokinetics of GSK3923868 following repeat inhaled administration in participants with asthma.
 
	
 
AUC(0-<math>\tau</math>) on Day 1 and Day 7 (<math>\tau=24</math>h for once a day dosing regimen) (if determined).
 
Cmax and Tmax on Day 1 and Day 7.
 

## 4. STUDY DESIGN

### 4.1. Overall Design

This is a 3-part, randomised, double-blind, placebo controlled, study designed to assess the safety, tolerability and PK of GSK3923868 administered as an inhalation powder blend (GSK3923868 capsules for inhalation) via Monodose inhaler in healthy participants (Parts A and B) and in participants with asthma (Part C).

In all parts, participants who meet the criteria for study entry will be randomised to receive GSK3923868 (active) or placebo before study intervention administration on Day 1.

As this study represents the first administration of GSK3923868 to humans, sentinel dosing will be utilised for each increasing dose level in Part A (if the selected dose level is below the previous dose level, sentinel dosing may still be applied) and before initiating full cohort repeat dosing in Part B. Each sentinel sub-cohort will consist of two participants receiving GSK3923868 or placebo (i.e. one will receive active and one will receive placebo). The decision to dose the remaining participants in each cohort will be based on the review of safety and tolerability data (i.e. AE/SAE, clinical safety laboratory assessments, vital signs, 12-lead safety ECGs and spirometry) from the sentinel sub-cohort by the Principal Investigator (PI) or appropriately qualified delegate, in consultation with the Medical Monitor. For Part A this will include data up to 24 hours post-dose and in Part B will include all data up to Day 14, 24 hours.

In addition, a Dose Escalation Committee (DEC) will be responsible for the review of emerging safety, tolerability and plasma PK results to determine the progression of single ascending dose levels in each treatment period in Part A and the progression to repeat dose levels in Parts B and C. Dose modification and escalation stopping criteria are outlined in Section 6.5 and the DEC committee structure is outlined in Section 10.1.5. Further information on the dose escalation process is outlined in the Dose Escalation Plan.

The total duration of study participation in each part of the study is summarised in [Table 1](#).

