**Table 1 Summary of study duration for study Parts A, B and C**

Part	Screening	Treatment Period	Washout Period	Follow-Up	Total Duration
A	Up to 30 days before the first dose.	Cohort 1 will be comprised of three treatment periods (3 days each) with a follow up phone call at 48 hours after each dose.	Will be at least 10 days between doses for each participant.	Between 7 to 14 days following the final dose.	Approx. 11 weeks
A		Cohort 2 will be comprised of three treatment periods (4 days each).			
B		Each participant will receive up to 14 days of treatment with additional observation up to 96 hours after their final dose.	N/A		Approx. 9 weeks
C		Each participant will receive up to 7 days of treatment.	N/A		Approx. 8 weeks

Each participant may only be randomised to one cohort and may only participate in one part of the study.

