## 7.3. Participant Discontinuation/Withdrawal from the Study

- A participant may withdraw from the study at any time at his/her own request or may be withdrawn at any time at the discretion of the investigator for safety, behavioural, or compliance reasons. This is expected to be uncommon.
- At the time of discontinuing from the study, if possible, the procedures outlined in the SOA on the day of discharge from the clinical unit should be completed (i.e. Days 2, 3, 18 and 8 for Parts A Cohort 1, A Cohort 2, B and C respectively).
- The participant will be permanently discontinued both from the study intervention and from the study at that time.
- If the participant withdraws consent for disclosure of future information, the Sponsor may retain and continue to use any data collected before such a withdrawal of consent.
- If a participant withdraws from the study, he/she may request destruction of any samples taken and not tested, and the Investigator must document this in the site study records.
- If participants prematurely discontinue in the study, they may be replaced at the discretion of the Medical Monitor in consultation with the Principal Investigator.

In Part A, the replacement participant will be assigned to the same treatment sequence and may start the treatment period where the last participant prematurely discontinued. In Parts B and C participants will be assigned to same treatment as the participant prematurely discontinued.

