4.3.2.1. Dose Proportionality	18
4.3.2.2. Accumulation and Steady State Assessment.....	19
4.3.2.3. Population PK Model	19
4.5. Other Analyses	22
4.5.1. Extent of Exposure	22
4.6. Interim Analyses	22
4.6.1. Dose Escalation Committee (DEC).....	22
4.6.2. Instream Analysis of PK Data	23
4.7. Changes to the Protocol Defined Statistical Analysis Plan	23
5. SAMPLE SIZE DETERMINATION	24
6. SUPPORTING DOCUMENTATION	26
6.1. Appendix 1 Abbreviations and Trademarks.....	26
6.1.1. List of Abbreviations	26
6.1.2. Trademarks	26
7. REFERENCES.....	27

Version history

This Statistical Analysis Plan (SAP) for study 213497 is based on the protocol dated 24-Sep-2021.

Table 1 SAP Version History Summary

SAP Version	Document Date	Protocol Version (Date) on which SAP is Based	Change	Rationale
1	-	07-Sep-2020	Not Applicable	Original version
2		24-Sep-2021	
 -Updated 'SABA only' treatment to include treatment with 'intermittent ICS/LABA' -Updated access to unblinded data from complete cohorts to include safety endpoints -Updated text to define time of unblinding -Cohorts 3 and 4 will be pooled and reported together 	
 -Population treatment requirements updated in line with updated treatment guidelines. -To allow better interpretation of both safety and PK data following the completion of each cohort, to help the design of future studies. -To enable modelling of PK data to start after cohort 3. -As cohorts 3 and 4 are identical cci [REDACTED] [REDACTED] [REDACTED], data from the two cohorts will be pooled and reported together.

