Study intervention	
The starting dose in Part A Cohort 1 Period 1 is 50 mcg.
 
The planned doses for dose escalation in Part A after the first cohort with 50 mcg are 100, 250, 500, 1000, and 3000 mcg. The planned dose for Part B (Cohorts 3 and 4) and Part C is 3000 mcg.
 
  
 Part	Screening	Treatment Period	Washout Period	Follow-Up	
   
 A	Up to 30 days before the first dose.	Each cohort will be comprised of three treatment periods (3 days each) with a follow up phone call at 48 hours after each dose.	Will be at least 10 days between doses for each participant.	Between 7 to 14 days following the final dose.	
 
 B	Each participant will receive up to 14 days of treatment with additional observation up to 96 hours after their final dose.	N/A	
 
 C	Each participant will receive up to 7 days of treatment.	N/A	
  
 
The total duration of the study will be approximately 11 weeks in Part A, approximately 9 weeks in Part B and approximately 8 weeks in Part C.
					Part	Screening	Treatment Period	Washout Period	Follow-Up	A	Up to 30 days before the first dose.	Each cohort will be comprised of three treatment periods (3 days each) with a follow up phone call at 48 hours after each dose.	Will be at least 10 days between doses for each participant.	Between 7 to 14 days following the final dose.	B	Each participant will receive up to 14 days of treatment with additional observation up to 96 hours after their final dose.	N/A	C	Each participant will receive up to 7 days of treatment.	N/A
Part	Screening	Treatment Period	Washout Period	Follow-Up																	
A	Up to 30 days before the first dose.	Each cohort will be comprised of three treatment periods (3 days each) with a follow up phone call at 48 hours after each dose.	Will be at least 10 days between doses for each participant.	Between 7 to 14 days following the final dose.																	
B		Each participant will receive up to 14 days of treatment with additional observation up to 96 hours after their final dose.	N/A																		
C		Each participant will receive up to 7 days of treatment.	N/A																		

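### The Part A primary-endpoint window ends on Day 2, a day before Cohort 2's Day 3 discharge, and conflicts with protocol 9.4.1.2

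*Protocol*

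**What the plan says.** **Endpoint window.** Protocol 1.1 and 3.1 and SAP 1.1.1.1 and 4.2 define the second primary endpoint as clinically significant laboratory, vital-sign, ECG and "spirometry measurements up to Day 2 of the final treatment period in Part A". The corresponding limits are Day 18 in Part B and Day 8 in Part C. Cohorts 1 and 2 are not distinguished.

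**Second window.** Protocol 9.4.1.2 says that clinically significant measurements at any time from randomisation to follow-up are reported as part of the primary endpoint.

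**Discharge.** Protocol 7.3 lists the discharge days as "Days 2, 3, 18 and 8 for Parts A Cohort 1, A Cohort 2, B and C respectively". Protocol Table 1 agrees: "Cohort 2 will be comprised of three treatment periods (4 days each", against three days in Cohort 1.

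**Sentinel review.** Protocol 1.1 and 4.1 set one review window for sentinel participants in both Part A cohorts: "For Part A this will include data up to 24 hours post-dose".

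**SAP design summary.** The SAP "is based on the protocol dated 24-Sep-2021". Its section 1.2 nevertheless says of Part A: "Each cohort will be comprised of three treatment periods (3 days each", with a phone call at 48 hours. SAP 4.7 declares no change from the protocol's planned analysis.

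**The concern.** The endpoint window appears meant to close at discharge. It does so in Cohort 1, Part B and Part C, but not in Cohort 2, whose participants stay a day longer. The discharge assessments after the last Cohort 2 dose therefore fall outside the window in the objectives tables and the SAP, but inside the window in protocol 9.4.1.2.

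The last Cohort 2 period is planned at 3000 mcg, the top single dose and the planned repeat dose for Parts B and C. With two windows for one primary endpoint, two programmers working from the same documents could produce different primary safety tables at that dose.

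**Working it through.** The plan states no figure for this point, so the check is of dates and counts.

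**1. Window end minus discharge day** (windows from protocol 3.1 and 3.2 and SAP 4.2; discharge from protocol 7.3):

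| Setting | Window ends | Discharge | Difference (days) |
|---|---|---|---|
| Part A Cohort 1 | Day 2 | Day 2 | 2 − 2 = 0 |
| Part A Cohort 2 | Day 2 | Day 3 | 2 − 3 = −1 |
| Part B | Day 18 | Day 18 | 18 − 18 = 0 |
| Part C | Day 8 | Day 8 | 8 − 8 = 0 |

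**2. Cross-check of the discharge day.** There is no Day 0. Days −1, 1 and 2 make 3 days; Days −1, 1, 2 and 3 make 4. Table 1 gives 3 for Cohort 1 and 4 for Cohort 2. Day 3 discharge in Cohort 2 therefore rests on running text and Table 1, without the detailed schedule.

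**3. Which periods are cut.** The window closes on Day 2 of the *final* period. Call the Period 6 dosing day 0, so that the window closes at +1. Doses are at least 10 days apart.
- Period 4, Day 3: at the latest −20 + 2 = −18. Inside.
- Period 5, Day 3: at the latest −10 + 2 = −8. Inside.
- Period 6, Day 3: +2. Outside, by one day.

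**4. How many.** Each Cohort 2 period has 12 participants, 9 active and 3 placebo (protocol Table 2 and 9.2). Cohort 2 has 12 × 3 = 36 participant-periods, 9 × 3 = 27 of them active. Affected: 12 of 36 (33.3%), and 9 of 27 active (33.3%). Those 9 are all the planned active participants at the 3000 mcg single dose.

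**5. Which measurements.** In the text copy of the Cohort 2 schedule, the last laboratory, vital-sign and ECG marks share a field with Discharge. Spirometry has no mark there. So the Day 3 values at issue appear to be laboratory, vital signs and ECG. This step, unlike steps 1 to 4, depends on the schedule.

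**6. The two windows compared.** The follow-up contact in protocol 1.3 is a telephone call with no laboratory, vital-sign, ECG or spirometry assessment scheduled. For scheduled measurements after the last dose, the two windows therefore differ only at Period 6 Day 3. They also treat repeat or unscheduled measurements after discharge differently in every part: 9.4.1.2 counts them and the shorter window does not.

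**7. Illustration.** One active participant whose only clinically significant value came on Period 6 Day 3 would change the 3000 mcg count from 0 of 9 to 1 of 9 (11.1%), depending on the window used.

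**The case against.** The strongest reply is that little turns on this. No hypothesis is tested (protocol 9.1). SAP 4.2.2.2 tabulates clinically significant values at each visit and names that table as the primary-endpoint display, so a scheduled Day 3 visit would probably appear in it. Adverse events are collected to follow-up (protocol 8.2.1), and clinically significant laboratory changes must be recorded as adverse events (8.1.5). Protocol 9.4.1.2 would count the Day 3 values in any case.

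Most of that stands, and it is why the point is minor. It does not settle which window governs: the SAP carries only the Day 2 limit, and its by-visit table sits under that endpoint definition. Adverse-event recording is not a full substitute either. SAP 4.2.1 defines clinical significance for laboratory values, vital signs and ECGs by fixed ranges of potential clinical interest, whereas an abnormal result becomes an adverse event through investigator judgement.

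A reader might go further and infer that Cohort 2 sentinel pairs have no post-dose laboratory result before the rest of the cohort is dosed. Protocol 4.1 bases that decision on "AE/SAE, clinical safety laboratory assessments, vital signs, 12-lead safety ECGs and spirometry" and adds "For Part A this will include data up to 24 hours post-dose". In the text copy of the Cohort 2 schedule, the row "Laboratory Safety Assessment" has its only post-dose mark in the discharge field. The documents do not support the inference. That copy leaves the Day 2 field blank in every point-assessment row, including PK, although protocol 4.3.1 requires PK to 24 hours; columns have also shifted in the Cohort 1 schedule. A blank laboratory cell there proves nothing. Moreover, 4.1 makes laboratory results an input to the decision, does not forbid waiting for them, and other sections allow retimed, unscheduled or additional tests (1.3, 8, Appendix 2).

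**Conclusion.** The Part A window is wrong as written for Cohort 2. It ends one day before discharge and conflicts with protocol 9.4.1.2. Taken literally, it excludes the Period 6 Day 3 assessments from the primary endpoint: 12 participants, 9 active, at a planned 3000 mcg.

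The severity is minor. A reader might infer that Day 3 data at 500 and 1000 mcg are also excluded, or that data are lost. Neither follows: Periods 4 and 5 lie inside the window, and the Day 3 values are collected and summarised whichever window applies. What is unsettled is whether they count as primary.

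The conclusion assumes that Cohort 2 runs all three planned periods at the planned doses; if it stopped early, the same gap would fall on whichever period was last. It also assumes that Day 3 carries laboratory, vital-sign and ECG assessments, as the schedule suggests.

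The 3-day period length in SAP 1.2 is a clerical mismatch. Exposure in SAP 4.5.1 is calculated from treatment dates, so no analysis uses it.

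**What to change.** 1. In protocol 1.1 and 3.1 and SAP 1.1.1.1 and 4.2, end the Part A window at Day 2 of the final treatment period for Cohort 1 and at Day 3 for Cohort 2.
2. Make protocol 9.4.1.2 agree, and say whether repeat or unscheduled values after discharge count.
3. As tidying only, correct SAP 1.2 to 4-day periods without the 48-hour call for Cohort 2.
4. As a query only, confirm the Day 2 laboratory cell for Cohort 2 in the original schedule. No change to the sentinel rule is proposed on present evidence.

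The cost of items 1 to 3 is protocol and SAP wording, with no added visit, sample or participant. Item 4 is one look at the source table.
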